### 2.2.3 Toxicology

The safety of NKTR-214 was evaluated in rats and cynomolgus monkeys for up to 6 weeks of every 14 day (q14d) administration (q14dx3). A PEG control was included in the rat GLP toxicity study. Biomarkers of NKTR-214 immune stimulation (peripheral lymphocyte counts and plasma sCD25 levels) were included in these studies. In addition, cardiovascular safety was evaluated in a telemetry study in cynomolgus monkeys. The monkey was identified as the most sensitive species (see Table 3). In addition, NKTR-214 binding affinity to the IL-2 receptor and T-cell activation was comparable in vitro between human cell lines and the cynomolgus monkey cell lines. Clinical observations in the monkey after each NKTR-214 dose included transient (and reversible) hypoactivity, decreased appetite, emesis, diarrhea, decreased fecal output, and hunched posture on Days 2-9 after each dose. Findings consistent with systemic immune

stimulation included transient and dose-related increased white blood cell (WBC) counts, largely due to the increase in lymphocytes, and an increase in sCD25 that were observed 5 to 7 days post each NKTR-214 dose, all of which returned to baseline 14 days postdose. Noteworthy histopathology findings in the monkey were minimal to mild inflammation in multiple organs (including liver, heart, and kidney), hematopoiesis in bone marrow, and hypercellularity in the thymus and spleen. These histopathologic changes partially or in some cases completely resolved on recovery (6 weeks post last dose). Of note, no evidence of cardiovascular effects such as ECG abnormalities, hypotension, pulmonary edema or vascular leak were found in the monkey at the NKTR-214 maximum tolerated dose (MTD) of 0.1 mg/kg in contrast to the reports of vascular leak at the MTD for aldesleukin ([Anderson, 1993](#)). The MTD of NKTR-214 was determined as 0.3 mg/kg in rats and 0.1 mg/kg in monkeys. Detailed descriptions of these studies and their results can be found in the NKTR-214 Investigator’s Brochure.

### 2.3 Starting Dose Rationale

The planned Phase 1 NKTR-214 starting dose of 0.003 mg/kg is 1/10th of the cynomolgus monkey MTD (0.1 mg/kg) that has been corrected for body surface area. A dose of 0.003 mg/kg is expected to be active in humans since it is the lowest dose tested in the monkey toxicology study at which increases in both sCD25 (10-fold) and lymphocyte counts (2-fold) were observed. A dosing schedule of q21d was chosen for the first in human study based on the histopathologic changes (inflammatory cell infiltrates) in monkeys 14 days after administration of the last q14d NKTR-214 dose that almost completely resolved with an additional 4 weeks of recovery (6 weeks following the last dose). [Table 3](#) shows the safety margins for the proposed clinical starting dose of NKTR-214.

**Table 3: Safety Margins for the Proposed Clinical Dose of NKTR-214**

Toxicity Study	Animal MTD (mg/kg)	HED (mg/kg) a	Safety Margin	Phase 1 Starting Dose (mg/kg)
6-week Rat (q14dx3)	0.3	0.05	17	0.003
6-week Monkey (q14dx3)	0.1	0.03	10	

- a. HED (Human Equivalent Dose) = (dose in animals)/(conversion factor). Conversion factor = 3.1 for monkeys and 6.2 for rats, based on body surface area differences per “FDA Guidance for Industry: Estimating the Maximum Safe Starting Dose in Initial Clinical Trials for Therapeutics in Adult Healthy Volunteers.” All NKTR-214 dose levels are expressed in IL-2 equivalents.

### 3.0 STUDY OBJECTIVES

#### 3.1 Primary Objective

The primary objectives are:

- To evaluate the safety and tolerability, and define the MTD of NKTR-214.
- To evaluate the efficacy of NKTR-214 by assessing the objective response rate (ORR) at the MTD or the dose below the MTD.

#### 3.2 Secondary Objectives

The secondary objectives are:

- To evaluate the efficacy of NKTR-214 by assessing best overall response (BOR), [REDACTED] duration of response (DOR), clinical benefit rate (CBR), time to response ([REDACTED])
- To characterize the pharmacokinetic (PK) profile of NKTR-214 and relevant metabolites.
- To assess the immunogenicity of NKTR-214.

#### 3.3 Exploratory Objectives

The exploratory objectives are:

- To assess the immunologic effect of NKTR-214 in tumor tissue on tumor-infiltrating lymphocytes (TIL).
- To assess the immunologic effects of NKTR-214 in blood, including effects on cytokines, NK cells, T-cells, and other serum proteins and immune modulators.

## 4.0 STUDY DESIGN

### 4.1 Summary of Study Design

This study is a multicenter Phase 1/2, open-label, dose escalation and dose expansion study of NKTR-214 in subjects with histologically confirmed locally advanced or metastatic solid tumors who have measurable disease. The study will be conducted in 3 parts (Part 1 Dose Escalation followed by Part 2 Dose Expansion).

#### 4.1.1 Screening

Up to 28 days.

#### 4.1.2 Open-label Treatment

##### 4.1.2.1 Part 1: Dose Escalation

Subjects will be enrolled in groups of at least 3 subjects in each cohort during the dose escalation phase.

The first dose to be studied will be 0.003 mg/kg administered as an IV infusion over 15 ( $\pm$  5) minutes every 21 days (q21d). Dose escalation will be carried out as listed in [Table 5](#). Dose levels for a given cohort, as listed in [Table 4](#), may be reduced by 25-50% depending on the severity, duration and frequency of toxicities as well as the PK profile, if available, observed at the previous dose level. A subject's dose level may not be escalated once assigned.

For each dose level, the first subject enrolled will be dosed on Cycle 1 Day 1 and monitored for safety and tolerability on Cycle 1, Days 1 through 5, before additional subjects are dosed.

In situations where a cohort of 3 subjects has been enrolled and additional subjects in screening have been deemed eligible for the study, these additional eligible subjects may be enrolled to the cohort. In the event of more than 3 subjects being enrolled to a cohort, the dose escalation decision will be made when the first 3 subjects in the cohort have completed their first cycle (i.e. completion of cycle or occurrence of a dose-limiting toxicity [DLT]). Moreover, the cohort safety review committee or Sponsor may determine that inadequate information has been obtained in a cohort of 3 subjects and to further understand the benefit/risk profile at a given dose level, additional subjects may be enrolled.

Additional subjects may be enrolled at other doses and frequencies deemed to be safe to more fully explore the safety, tolerability, pharmacokinetics, biomarker assessments, and preliminary efficacy of NKTR-214. These additional cohorts of up to 12 subjects may be enrolled to further evaluate NKTR-214 at the recommended phase 2 dose or at doses at or below the MTD.

During dose escalation, subjects who are withdrawn from the study during Cycle 1 for reasons other than occurrence of a DLT will be replaced.

A DLT is defined as a Grade 3 or higher study drug-related or possibly related AE occurring within the first cycle of dosing (excluding Grade 3/4 transient lymphopenia < 14 days in duration, tumor flare defined as local pain, irritation, or rash localized at sites of known or suspected tumor, a transient, reversible  $\leq$  grade 3 infusion AE [ $<$  24 hours], non-clinically significant laboratory abnormalities, or fatigue lasting less than 72 hours) using National Cancer Institute (NCI) Common Terminology Criteria for AEs (CTCAE) version 4.03.

All drug related AEs after Cycle 1 will continue to be collected and evaluated by the Investigators and the Sponsor on an ongoing basis and may be taken into consideration in determining the MTD.

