### Dose Escalation Scheme

For each dose level, the first subject enrolled to the dose cohort will be treated and monitored from Cycle 1, Day 1 through Cycle 1, Day 5 for tolerance prior to the dosing of additional subjects at that dose level. The first subject enrolled to the study will be administered NKTR-214 at the first dose level of 0.003 mg/kg (**Table 4**). Enrollment into the next cohort cannot begin until a full cycle has elapsed since the last subject's first dose in the previous cohort. If no DLTs occur in a cohort of 3 subjects, a new cohort of 3 subjects will be treated at the next higher dose level (**Table 5**). If only 1 of 3 subjects in a cohort experiences a DLT, that cohort will be expanded to 6 subjects. If only 1 of the 6 subjects experiences a DLT, then the next cohort of 3 subjects will be treated at the next higher dose level. If 2 or more subjects within a cohort experience DLTs, then that dose level will be above the MTD (the highest dose tested where no more than 1 of 6 subjects has experienced a DLT), and new subjects will be enrolled at the previous lower (tolerated) dose level until that cohort has 6 subjects. A subject who is withdrawn from the study during Cycle 1 for reasons other than a DLT will be replaced. Approximately 50 subjects will be enrolled into the dose escalation phase of the study.

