**Table 5: Dose Escalation Rules**

Number of Subjects with DLT at a Given Dose Level	Dose Escalation Decision Rule
0 out of 3	Enter 3 subjects at the next higher dose level.
1 out of 3	Will enter at least 3 more subjects at this dose level. If 0 of these additional 3 subjects experience a DLT, will proceed to the next dose level. If 1 or more of this group suffers a DLT, then the dose escalation is stopped, and this dose is declared the MAD. Three (3) additional subjects will be entered at a lower dose level if only 3 subjects were treated previously at that dose.
$\geq 2$	Dose escalation will be stopped. This dose level will be declared the MAD (highest dose administered). Three (3) additional subjects will be entered at a lower dose level if only 3 subjects were treated previously at that dose.
$\leq 1$ out of 6 at highest dose level below the maximally administered dose	This is the MTD. At least 6 subjects must be entered at the recommended dose for the phase 2 recommended dose.

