## **6.9 Determination of Dose-Limiting Toxicities**

Based on the preclinical toxicology data and the anticipated half-life of NKTR-214 (15-20 hours), drug-related toxicity is most likely to occur during treatment or within 10 days following treatment. Based on this, dose-limiting toxicities (DLTs) will be assessed in the first cycle for all subjects enrolled to a specific cohort (same dose level). If DLTs are not observed, dose escalation will be permitted and enrollment will begin at the next successive ascending dose cohort. Intra-subject dose escalation will not be permitted. Dose reduction is allowed in subjects based on toxicity with approval from the Medical Monitor.

Unless otherwise suggested by clinical data, a dose-limiting toxicity (DLT) is defined as a Grade 3 or higher study drug-related or possibly related AE occurring within the first cycle of dosing (excluding Grade 3/4 transient lymphopenia < 14 days in duration, tumor flare defined as local pain, irritation, or rash localized at sites of known or suspected tumor, a transient, reversible  $\leq$  grade 3 infusion AE, non-clinically significant laboratory abnormalities, or fatigue lasting less than 72 hours) using NCI CTCAE version 4.03.

Delayed DLTs are drug-related adverse events that occur after Cycle 1. Delayed DLTs will not be used to determine the MTD for dose escalation. Delayed DLTs will be collected and evaluated by the Investigators and the Sponsor on an ongoing basis.

All drug related adverse events after Cycle 1 will continue to be collected and evaluated by the Investigators and the Sponsor on an ongoing basis and will be taken into consideration in determining the MTD.

All AEs that meet DLT criteria, as well as any  $\geq$  Grade 3 immune-related adverse event (regardless of attribution), must be reported to the Sponsor, within 24 hours using the same rapid notification procedures that are used for serious AEs (Section 8.7).

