3 STUDY DESIGN AND PLAN

This is a Phase 1/2, open-label, multicenter, dose escalation and dose expansion study of NKTR-214 in subjects with histologically confirmed locally advanced or metastatic malignancies who have measurable disease. The study will consist of a dose escalation phase and a dose expansion phase.

The 3+3 design will be used as a guide to determine the MTD in the dose escalation phase. Additional eligible subjects may be enrolled into the cohort for which the first three subjects are under dose-limiting toxicity (DLT) observation. However, the dose escalation decision will be made when the first 3 subjects in the cohort have completed their DLT observation period. During

the dose escalation period, subjects who are withdrawn from the study during the DLT observation period due to reasons other than toxicity will be replaced. All drug related AEs, including events beyond the DLT observation period, will be taken into account to determine the MTD.

Once the MTD has been reached, lower dose and different dose schedules may be assessed.

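### For an escalation cohort of 4 or 5, the plan ties the decision to the first 3 subjects, conflicts with its own Section 6.9, and gives no action for a single DLT in subject 4 or 5

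*Protocol*

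**What the plan says.** Protocol 4.1.2.1 lets eligible subjects already in screening join a cohort that has its three. For that situation it states that "the dose escalation decision will be made when the first 3 subjects in the cohort have completed their first cycle", where a DLT also counts as completion. SAP Section 3 repeats the rule: "the dose escalation decision will be made when the first 3 subjects in the cohort have completed their DLT observation period".

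Other text looks at the whole cohort:

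- Dose Escalation Scheme, waiting rule: "Enrollment into the next cohort cannot begin until a full cycle has elapsed since the last" subject's first dose in the cohort before it.
- Dose Escalation Scheme, stopping rule: "If 2 or more subjects within a cohort experience DLTs, then that dose level will be above the MTD".
- Protocol 6.9: DLTs "will be assessed in the first cycle for all subjects enrolled to a specific cohort (same dose level"). It then permits escalation where none is observed.
- Table 5 heads its left-hand column "Number of Subjects with DLT at a Given Dose Level".

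The one-DLT rule is written for three subjects only: "If only 1 of 3 subjects in a cohort experiences a DLT, that cohort will be expanded to 6 subjects". Table 5 has entries for 0 of 3, 1 of 3, 2 or more, and at most 1 of 6. The synopsis table has the same rows.

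**The concern.** Suppose four subjects are treated, the first three have no DLT and the fourth has one. Under 4.1.2.1 and SAP Section 3 the decision rests on the first three, and the row of Table 5 for 0 of 3 says escalate. Had the DLT fallen in subject 1, 2 or 3, the same 1-in-4 result would have expanded the cohort to six. Enrolment order carries no information about toxicity, so it should not decide between the two actions.

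At stake is one escalation step in a first-in-human study whose visible dose levels double (0.003, 0.006, 0.012 mg/kg). The next cohort could receive a higher dose on weaker evidence than the plan requires when a DLT occurs among the first three. Two people applying the plan to identical data could also reach different decisions.

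**Working it through.** **Texts side by side, for 0 DLTs in the first 3 and exactly 1 in subject 4 or 5**

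| Source | What it yields |
|---|---|
| 4.1.2.1 and SAP 3, with the 0-of-3 row of Table 5 | Escalate, on the literal reading |
| Protocol 6.9 | Does not clear escalation, because a DLT was observed; names no next step |
| Dose Escalation Scheme | Higher dose waits for the last subject's cycle; no action for 1 of 4 or 1 of 5 |
| Table 5 | No row |

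Section 6.9 cannot simply be taken as the governing rule. Read strictly it would not clear 1 of 6 either, and the Dose Escalation Scheme expressly lets 1 of 6 escalate.

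**Inputs.** The plan gives no operating characteristics for the escalation rule, so there is no stated figure to reproduce; Tables 7 and 8 concern expansion only. The true DLT rate p is an assumption. I use 10%, 25%, 30% and 33%. The only toxicity rate in the documents is the 30% target for expansion. Subjects are taken as independent, and q = 1 − p.

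**Order alone, no rate needed.** If a DLT is equally likely in any subject, a single DLT in n subjects falls after the first three with probability (n − 3)/n. That is 1/4 = 25% for n = 4 and 2/5 = 40% for n = 5.

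**Probability of the uncovered case**

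- n = 4: p·q³
- n = 5: 2p·q⁴

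**Probability of escalating past the dose**

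- First-3 reading, with the stop at 2 or more in the cohort honoured: n = 4, q³ + 3p·q⁵; n = 5, q³(1 − p²) + 3p·q⁵.
- All subjects counted (1 of 4 or 1 of 5 is filled to 6, and escalates only if no further DLT occurs): n = 4, q⁴ + 4p·q⁵; n = 5, q⁵ + 5p·q⁵.

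Example, p = 0.33, n = 4: the first-3 reading gives 0.3008 + 0.99 × 0.1350 = 0.434. Counting all gives 0.2015 + 1.32 × 0.1350 = 0.380.

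| p | n | Uncovered case | Escalate, first-3 reading | Escalate, all counted | Difference |
|---|---|---|---|---|---|
| 0.10 | 4 | 0.073 | 0.906 | 0.892 | 0.014 |
| 0.10 | 5 | 0.131 | 0.899 | 0.886 | 0.013 |
| 0.25 | 4 | 0.105 | 0.600 | 0.554 | 0.046 |
| 0.25 | 5 | 0.158 | 0.573 | 0.534 | 0.040 |
| 0.30 | 4 | 0.103 | 0.494 | 0.442 | 0.052 |
| 0.30 | 5 | 0.144 | 0.463 | 0.420 | 0.043 |
| 0.33 | 4 | 0.099 | 0.434 | 0.380 | 0.055 |
| 0.33 | 5 | 0.133 | 0.402 | 0.358 | 0.044 |

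Differences are taken before rounding.

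**Check.** The difference should equal the chance of the uncovered case times the chance of a further DLT while filling to six. For n = 4 this is p·q³(1 − q²); at p = 0.25, 0.1055 × 0.4375 = 0.046. For n = 5 it is 2p·q⁴ × p; at p = 0.25, 0.1582 × 0.25 = 0.040. Both agree with the table.

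**Six enrolled.** Both rules give q⁶ + 6p·q⁵ (0.534 at p = 0.25, 0.358 at p = 0.33), because 1 of 6 escalates either way. The difference is zero.

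**The case against.** The strongest reply is that the plan never tells anyone to disregard a DLT in subject 4 or 5. In 4.1.2.1 the word *when* can be read as setting the timing of the decision, not the data that count. Table 5 counts DLTs at a dose level. Section 6.9 assesses the whole cohort and withholds its permission once a DLT is seen. SAP Section 3 also takes all drug-related events, including later ones, into account for the MTD. A reader might infer that no rule at all stands between such a DLT and escalation. That goes too far: on plain wording the case is unassigned, not cleared.

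This stands, and it narrows the point without removing it. Even if later DLTs count, the plan still does not say what one DLT in four or five triggers, and 6.9 and 4.1.2.1 still point in different directions.

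Two other strong readings also fail. A reader might infer that the next cohort could be dosed before the DLT window of subject 4 or 5 has closed; the waiting rule prevents that. Or that an MTD could be wrongly declared; the MTD tolerates no more than 1 DLT in 6, and Table 5 adds: "At least 6 subjects must be entered at the recommended dose for the phase 2 recommended dose".

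The size is also fairly challenged. Rates of 25% to 33% lie near where the difference is largest, and at 10% it is under 1.5 points. Over-enrolment to exactly four or five is needed, and its frequency is unknown. The next dose may be cut by 25% to 50%, the safety committee or sponsor may add subjects, and the SAP treats the 3+3 design as a guide. All of these are discretionary, and none is tied to this event. Finally, counting everyone would still escalate often in the uncovered case: q² = 45% to 56% of 1-in-4 results and q = 67% to 75% of 1-in-5 results at rates of 33% to 25%.

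**Conclusion.** The point holds as an unresolved conflict between 4.1.2.1 (with SAP Section 3) and 6.9, together with a missing action for one DLT in four or five subjects. On the literal 4.1.2.1 reading, the order of enrolment decides whether the same result leads to expansion or escalation.

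The effect is modest: 1.3 to 1.4 percentage points more chance of escalating past the dose at a 10% DLT rate, and 4.0 to 5.5 points at 25% to 33%. These figures assume a cohort of four or five, the literal reading, independent subjects, the assumed rates, and no use of the discretionary safeguards. The exposure is limited to one escalation step. It is worth correcting because this is a first-in-human study and the change is almost entirely one of wording.

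**What to change.** In Protocol 4.1.2.1 and SAP Section 3, state that the escalation decision is made when every subject enrolled at that dose level before the decision has completed Cycle 1 or had a DLT, and that DLTs in all of those DLT-evaluable subjects count. State also that later additional cohorts of up to 12 subjects fall outside this rule. Without that limit they could trip the stop at 2 or more too easily: at an assumed 10% rate, 12 subjects give at least two DLTs with probability 1 − 0.9¹² − 12 × 0.1 × 0.9¹¹ = 34%.

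In Table 5 and the synopsis table, use these rows:

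| DLTs at the dose level | Action |
|---|---|
| 0 in 3 or more | Escalate |
| 1 in 3, 4 or 5 | Expand to at least 6; escalate only if no further DLT occurs |
| 1 in 6 or more | Escalate |
| 2 or more | Stop, as now |

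Align Section 6.9 with these rows. Leave the waiting rule and the six-subject requirement for the recommended dose as they are.

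The waiting rule already imposes the delay until the last subject's cycle ends. The added cost arises only after 0 of 3 followed by a single DLT: two more subjects for 1 of 4, or one more for 1 of 5, and their Cycle 1 window (21 days on the q21d schedule). At the four assumed rates that is 7% to 11% of cohorts of four and 13% to 16% of cohorts of five.

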### Dose Escalation Scheme

For each dose level, the first subject enrolled to the dose cohort will be treated and monitored from Cycle 1, Day 1 through Cycle 1, Day 5 for tolerance prior to the dosing of additional subjects at that dose level. The first subject enrolled to the study will be administered NKTR-214 at the first dose level of 0.003 mg/kg (**Table 4**). Enrollment into the next cohort cannot begin until a full cycle has elapsed since the last subject's first dose in the previous cohort. If no DLTs occur in a cohort of 3 subjects, a new cohort of 3 subjects will be treated at the next higher dose level (**Table 5**). If only 1 of 3 subjects in a cohort experiences a DLT, that cohort will be expanded to 6 subjects. If only 1 of the 6 subjects experiences a DLT, then the next cohort of 3 subjects will be treated at the next higher dose level. If 2 or more subjects within a cohort experience DLTs, then that dose level will be above the MTD (the highest dose tested where no more than 1 of 6 subjects has experienced a DLT), and new subjects will be enrolled at the previous lower (tolerated) dose level until that cohort has 6 subjects. A subject who is withdrawn from the study during Cycle 1 for reasons other than a DLT will be replaced. Approximately 50 subjects will be enrolled into the dose escalation phase of the study.

**Table 4: Part 1: Sample Dose Escalation Scheme**

Cohort	NKTR -214 Dose
Cohort 1	0.003 mg/kg
Cohort 2	0.006 mg/kg
Cohort 3	0.012 mg/kg
██████	██████
██████	██████
██████	██████

The Sponsor and at least one Investigator will jointly decide the following:

- Dose levels for a given cohort, as listed in **Table 4**, may be reduced by 25-50% depending on the severity, duration, and frequency of toxicities observed at the previous dose level as well as the PK profile, if available.
- In the event that MTD is not determined at the highest dose level listed in the table, dose escalation at no more than 100% higher than previous dose may continue.
- The schedule of dosing can be modified to every 14 or 28 days based on a review of the safety data and available PK data.
  - Note, the first dose level for every 14-day cohort will be determined as follows:  
If MTD has been reached in the 21-day dosing cohort, the dosing level will be at least one dose lower than MTD. If MTD has not been reached in the 21-day dosing cohort, the dosing level will be at least one dose lower than the highest dosing cohort tested in the 21-day dosing cohort.
  - The first dose level for every 28-day cohort will be either the MTD using the 21-day dosing cohort (if determined) or the highest dosing cohort tested in the 21-day dosing cohort (if MTD not determined).
- Once the MAD has been reached, lower doses and different dose schedules may be assessed, within the anticipated total number of subjects of approximately 50.

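### Minor: the q28d starting-dose rule does not exclude a level declared the MAD, so read literally it can name a dose that the same section places above the MTD

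*Protocol*

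**What the plan says.** All of the relevant rules are in Protocol Section 4.1.2.1, except the last two items.

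- **q28d start.** The first q28d level is the q21d MTD if one has been determined, "or the highest dosing cohort tested in the 21-day dosing cohort (if MTD not determined".
- **q14d start.** The neighbouring rule for the case without an MTD steps down: "the dosing level will be at least one dose lower than the highest dosing cohort tested in the 21-day dosing cohort".
- **MAD.** Table 5 stops escalation at 2 or more DLTs: "This dose level will be declared the MAD (highest dose administered". A level with 1 DLT in 3 and at least 1 more in the added subjects is also the MAD.
- **MTD.** Table 5 requires at most 1 DLT "out of 6 at highest dose level below the maximally administered dose". If the lower level has only 3 subjects, 3 more are entered there.
- **Enrolment after failure.** The Dose Escalation Scheme text says that a level with 2 or more DLTs lies above the MTD. It sends new subjects to the preceding tolerated level until that level has 6.
- **Other schedules.** The notes under Table 4 say: "Once the MAD has been reached, lower doses and different dose schedules may be assessed". Elsewhere the section limits other doses and frequencies to those judged safe, and limits the additional cohorts to the recommended Phase 2 dose or doses no higher than the MTD.
- **SAP Section 3** places other schedules after the MTD has been reached, not after the MAD.
- **Protocol Section 6.9** expects drug-related toxicity during treatment or in the 10 days after it.

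**The concern.** A starting-dose rule should give an acceptable dose in every state in which it can be applied. The q28d fallback depends only on whether the MTD has been determined. That condition covers two different situations: no toxic level has been met yet, or a toxic level has been met and no tolerated level has been established below it. In the first, the highest cohort tested is a reasonable start. In the second, it is the level that stopped escalation.

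The longer interval does not protect subjects in the DLT period. Cycle 1 contains one dose on either schedule, and the 10-day window in Section 6.9 is shorter than both 21 and 28 days. Cycle 1 exposure at the MAD would therefore be the same under q28d as under q21d.

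**Working it through.** The documents state no figure on this point, so there is none to reproduce. The check traces the rules through each possible q21d state.

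| q21d state | MTD determined? | Highest q21d cohort tested | Literal q28d start | Literal q14d start | New subjects under the Dose Escalation Scheme |
|---|---|---|---|---|---|
| No level has failed | No | A level that has not failed | That level | At least one level lower | Escalation continues |
| MAD declared; level below has at most 1/6 | Yes | MAD | The MTD (level below) | At least one below the MTD | No backfill needed |
| (a) MAD declared; level below at 0/3 and being filled to 6 | No | MAD | **MAD** | At least one below the MAD | Level below |
| (b) No q21d level tolerated, e.g. the first level fails | No | MAD | **MAD** | At least one below the MAD | No lower tolerated level exists |

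The rule gives a sensible answer in the first two rows and names the MAD in the last two. State (a) is clearest when no lower level at all has 6 subjects. If a still lower level already has at most 1/6, the text definition of the MTD could be read as already met.

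State (a) can be reached on paper because the notes open other schedules at the MAD. It lasts while 6 − 3 = 3 further subjects are enrolled at the lower level and the last of them completes a 21-day first cycle. It lasts longer if the backfilled level fails.

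**Size at the listed doses.** Inputs from Table 4 are 0.006 and 0.012 mg/kg. Suppose 0/3 DLTs at 0.006 and 2 or more at 0.012.

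- Literal q28d start: 0.012 mg/kg. Literal q14d start: 0.006 mg/kg or lower. Backfill level: 0.006 mg/kg.
- Ratio of q28d start to tolerated level: 0.012 / 0.006 = 2.0.
- Upper level reduced by 25%, as the notes allow: 0.012 × 0.75 = 0.009, and 0.009 / 0.006 = 1.5.
- Upper level reduced by 50%: 0.012 × 0.5 = 0.006, ratio 1.0, so no excess.
- Beyond the table the notes permit "dose escalation at no more than 100% higher than previous dose may continue", so the ratio is at most 2.0. The redacted levels are unknown.

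In state (b) no ratio can be formed, because there is no tolerated level to compare with.

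**The case against.** The strongest reply is that the rest of the section already prevents this.

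1. After 2 or more DLTs, new subjects go to the lower level until it has 6. If that is followed, none are left for a q28d cohort at the MAD during the backfill.
2. Enrolment into the next cohort must wait a full cycle after the last subject's first dose in the previous one. If that covers a q28d cohort, the lower level will have either yielded an MTD or failed by the time q28d opens.
3. The same notes use the key phrase in a benign sense: "In the event that MTD is not determined at the highest dose level listed in the table, dose escalation" may continue. There, an undetermined MTD means that no level has failed. Read consistently, the highest cohort tested is then a tolerated one.
4. The limits to doses judged safe and no higher than the MTD, and the SAP's placing of other schedules after the MTD, point the same way.
5. The change is optional: "The schedule of dosing can be modified to every 14 or 28 days based on a review of the safety data" and available PK data.

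Much of this stands. It shows the probable intent and makes case (a) unlikely in practice. But these provisions contradict the starting-dose sentence and do not amend it. The q28d sentence does not say that it applies only when no level has failed. None of the provisions supplies a q28d start in case (b), where there is no lower tolerated level to backfill.

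**Conclusion.** The clause is wrong as written, and the point is minor. In cases (a) and (b) it names a level that the same section places above the MTD. In the listed-dose example for case (a), that level is 2.0 times the tolerated dose. The conclusion rests on reading an undetermined MTD literally, against the at-most-1-in-6 criterion, and on Table 5's description of the MAD as the highest dose given.

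Two stronger readings are tempting and are not supported.

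- A reader might infer that the protocol requires q28d subjects to be dosed at a toxic level. It does not. The schedule change is optional, follows joint review, and sits beside rules that direct subjects elsewhere.
- A reader might infer that the problem is likely to occur, because most 3+3 escalations pass a level on 0/3. With cohorts of exactly 3 and an assumed DLT rate p at the lower level, the share of escalations resting on 0/3 is (1−p)³ / [(1−p)³ + 3p(1−p)⁵] = 1 / [1 + 3p(1−p)²]. This is 0.88 at p = 0.05 and 0.69 at p = 0.30. But it is not the chance that a q28d cohort opens during the backfill, which the documents do not allow one to estimate. Section 4.1.2.1 also permits more than 3 subjects in a cohort, so the lower level may already have 6. No probability of harm can be derived.

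**What to change.** Replace the second branch of the q28d rule in the notes under Table 4 with wording such as:

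*or, if the MTD is not determined, the highest q21d level tested that has not been declared the MAD and has not otherwise had 2 or more subjects with a DLT; if there is no such level, a dose below the lowest level tested.*

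This keeps the likely intent when no level has failed. It gives 0.006 mg/kg in the worked example and covers failure at the first level. The sentence that opens other schedules once the MAD is reached can stay.

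The cost is a possibly lower q28d starting dose and one wording change carried in a protocol amendment with the usual ethics review. The synopsis and the SAP do not carry the q28d starting rule, so neither needs editing.
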